Subjects must be followed for at least 100 days after the last dose of blinded study therapy. Follow-up (FU1) occurs approximately 35 days (+/- 7 days) after last dose of coinciding with the date of discontinuation (+/- 7 days) if the date of discontinuation is greater than 35 days after the last dose. Follow up visit 2 (FU2) occurs approximately 80 days (+/- 7 days) after FU1. Survival visits are every 3 months from FU2 up to 5 years and may be conducted during a clinic visit or via the phone. The endpoint of this study is OS, and so tracking reporting the subject's status in the follow up setting according to the protocol guidelines for disease progression and survival are critical to the final study analysis. The importance of follow up should be clearly communicated to study subjects.

If blinded study drug(s) is discontinued prior to the subject's completion of the study, the reason for the discontinuation must be documented in the subject's medical records and entered on the appropriate case report form (CRF) page.

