4.5.3.3 Criteria to Resume Treatment

Subjects may resume treatment with blinded study therapy when the drug-related AE(s) resolve to Grade ≤ 1 or baseline value, with the following exceptions:

- Subjects may resume treatment in the presence of Grade 2 fatigue
- Participants who have not experienced a Grade 3 drug-related skin AE may resume treatment in the presence of Grade 2 skin toxicity
- Subjects with Grade 2 AST/ALT and/or total bilirubin abnormalities may resume treatment when laboratory values return to baseline and management with corticosteroids, if needed is complete.
- Subjects with a combined Grade 2 AST/ALT AND Total Bilirubin values meeting discontinuation criteria (section 4.5.3.4) should have treatment permanently discontinued
- Drug-related pulmonary toxicity, diarrhea, or colitis, must have resolved to baseline before treatment is resumed. Subjects with persistent Grade 1 pneumonitis after completion of steroid taper over at least 1 month may be eligible for retreatment if discussed with and approved by the BMS Medical Monitor
- Drug-related endocrinopathies adequately controlled with only physiologic hormone replacement may resume treatment after consultation with the BMS Medical Monitor. Adrenal insufficiency requires discontinuation regardless of control with hormone replacement.

If the criteria to resume treatment are met, the subject should restart treatment at the next scheduled timepoint per protocol. Doses should not be skipped. In particular, this is to ensure that subjects in Arm B will receive 4 administrations of combined nivolumab and ipilimumab treatment if toxicity allows.

If treatment is delayed > 6 weeks (42 days) from the last dose due to blinded study drug-related toxicity, the subject must be permanently discontinued from blinded study therapy, except as specified in Section 4.5.3.4. In the event treatment is delayed > 6 weeks due to reasons other than blinded study drug-related toxicity, the case should be discussed with the Medical Monitor before proceeding.

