 - Dosing delays to allow for prolonged steroid tapers to manage drug-related AEs are allowed. Prior to re-initiating treatment in a subject with a dosing delay lasting > 6 weeks from the last dose, the BMS Medical Monitor must be consulted
 - Dosing delays > 6 weeks from the last dose that occur for non-drug-related reasons may be allowed if approved by the BMS Medical Monitor
- Any AE, laboratory abnormality, or intercurrent illness which, in the judgment of the Investigator, presents a substantial clinical risk to the subject with continued blinded study therapy dosing

Tumor assessments for all subjects should continue as per protocol even if blinded study therapy dosing is delayed. Periodic study visits to assess safety and laboratory studies should continue at least every 6 weeks or more frequently if clinically indicated during such dosing delays.

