Additional Exploratory Biomarker Testing						
Serum Whole Blood Tumor Biopsy			See Note			See Table 5.6-1 of Biomarker Sampling Schedule
PK and Immunogenicity Assessments						
PK samples			See Note			See Table 5.5-1 of PK and Immunogenicity Sampling
Immunogenicity samples			See Note			See Table 5.5-1 of PK and Immunogenicity Sampling
Outcomes Research Assessments						
Patient Reported Outcomes (PRO)	X		X	X	X	For on-treatment visits: Assessments (Lung Cancer Symptom Scale and EQ-5D) will be performed on treatment day prior to study treatment.
Health Resource Utilization	X		X	X	X	Except cycle 1. Note that concomitant medication collection will be included.

Table 5.1-2: On-Treatment Assessments for All Subjects, Cycle 1-2 [Cycle length 42 days]

Procedure	Cycle 1-2 Day 1	Cycle 1 Day 8	Cycle 1-2 Day 15	Cycle 1-2 Day 22	Cycle 1-2 Day 29	Notes
Clinical Drug Supplies						
Randomization	X					Call IVRS for randomization
Administer Blinded Study Drug	X		X	X	X	IVRS should be called within 1 day prior to blinded study therapy administration to receive vial assignment. Note: The subject must receive the blinded study medication within 3 business days after vial assignment. See section 4.5.1 for minimum dosing intervals between Cycles. A call to IVRS is made for every dosing visit.

Table 5.1-3: On-Treatment Assessments for All Subjects, Cycle 3 and subsequent cycles [Cycle 3+ length 14 days] (CA209451)

Procedure	Cycle 3 and subsequent cycles, Day 1	Notes
Safety Assessments		
Targeted Physical Examination	X	Within 72 hours prior to dosing
Vital Signs and Oxygen Saturation	X	Temperature, BP, HR, O2 saturation at rest by pulse oximetry at rest (also monitor amount of supplemental oxygen if applicable) within 72 hours prior to dosing and at any time a subject has any new or worsening respiratory symptoms
Physical Measurements	X	Includes Weight and ECOG performance status within 72 hours prior to dosing
Adverse Events Assessment	Continuously	Assessed using NCI CTCAE v. 4.0. SAEs should be approved in TAO within 5 days from entry
Review of Concomitant Medications	X	

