Patient Reported Outcomes (PRO)	X	For on-treatment visits: Assessments (Lung Cancer Symptom Scale and EQ-5D) will be performed on treatment day prior to study treatment. Assessments will be performed at each cycle on Day 1 for the remainder of the first 6 months on study, then every 6 weeks thereafter for the remainder of the treatment period.
Health Resource Utilization	X	Except cycle 1. Note that concomitant medication collection will be included.
Clinical Drug Supplies		
Administer Blinded Study Drug	X	IVRS should be called within 1 day prior to blinded study drug administration to receive vial assignment. Note: The subject must receive the blinded study therapy within 3 business days of vial assignment. See Section 4.5.1 for minimum dosing intervals between Cycles. A call to IVRS is made for every dosing visit.

Table 5.1-4: Follow-Up Assessments for All Subjects (CA209451)

Procedure	Follow-Up ^a Visits 1 and 2	Survival Follow-Up ^b Visits	Notes
Safety Assessments			
Targeted Physical Examination	X		To assess for potential late emergent study drug related issues
Adverse Events Assessment	X	X	NSAEs and SAEs must be collected up to 100 days after blinded study drug discontinuation. SAEs that relate to any later protocol specified procedure must be collected. SAEs should be approved in TAO within 5 days from entry.
Review of Concomitant Medication	X	X	Collection of concomitant medications only for treatment-related AEs or SAEs until the medication is discontinued.
Extended Laboratory Tests	X		CBC with differential, uric acid, BUN or serum urea level, serum creatinine, sodium, potassium, calcium, magnesium, chloride, phosphorus, bicarbonate (optional), amylase or lipase, glucose, AST, ALT, total bilirubin, alkaline phosphatase, LDH
Thyroid Function Testing	X		TSH (reflex to free T3 and free T4 if abnormal result)
Pregnancy Test	X		Serum or urine
Efficacy Assessments			
Radiographic Tumor Assessment CT/MRI	See Note	See note	See Table 5.4-1 for CT/MRI
Outcomes Research Assessments			
Patient Reported Outcomes (PRO)	X	EQ-5D only	Both the Lung Cancer Symptom Scale and EQ-5D will be given in FU Visits 1 & 2. In Survival Visits, EQ-5D is collected every 3 months for the first year of the Follow-up Phase, then every 6 months thereafter. For Survival Visits these can be collected in person or via telephone contact.
Healthcare resource utilization	X		

Table 5.1-4: Follow-Up Assessments for All Subjects (CA209451)

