Procedure	Follow-Up ^a Visits 1 and 2	Survival Follow-Up ^b Visits	Notes
Exploratory Biomarker Testing			
Serum	See Note.		Collection of Biomarker samples at time of progression is optional. See Table 5.6-1 of Biomarker Sampling Schedule.
Whole Blood			
Tumor Biopsy			
Subject Status			
Survival Status	X	X	Every 3 months after X02; may be accomplished by visit or phone contact, to update survival information and assess subsequent anti-cancer therapy.

^a Follow-up visits occur as follows: X01 = 35 days ± 7 days from last dose, X02 = 80 days ± 7 days from X01

^b Survival visits continue every 3 months ± 14 days after Follow-up Visit 2 until death, lost to follow-up, or withdrawal of study consent

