### 7.11.1 LCSS questionnaire

LCSS questionnaire completion rate, defined as the proportion of questionnaires actually received out of the expected number (i.e., the number of subjects still on treatment or in follow-up), will be calculated and summarized at each assessment point.

Baseline and change from baseline of the average symptom burden index score at each assessment point will be summarized using descriptive statistics (N, mean, median, SD, 25th and 75th percentiles) by treatment group, as randomized.

Kaplan-Meier plots for TTSD as measured by LCSS ASBI will be presented along with median TTSD and corresponding 95% CI. Hazard ratios and corresponding two-sided 95% CI will be estimated using unstratified Cox proportional hazard model, with treatment group as a single covariate. TTSD rates at fixed timepoints Week 6, 12 and 24 will be derived from the Kaplan Meier estimate and corresponding confidence interval will be derived based on Greenwood formula for variance derivation and on log-log transformation applied on the survivor function  $S(t)$ .

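### No LCSS or EQ-5D is scheduled while dosing is held, so the questionnaires tend to miss the worst of a toxicity that triggers a hold

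*Protocol*

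**What the plan says.** **When questionnaires are taken.** The patient-reported outcome rows of Protocol Tables 5.1-2 (Cycles 1-2, Days 1, 15, 22 and 29) and 5.1-3 (Cycle 3 onward) carry the same note: "Assessments (Lung Cancer Symptom Scale and EQ-5D) will be performed on treatment day prior to study treatment". Table 5.1-3 adds "Assessments will be performed at each cycle on Day 1 for the remainder of the first 6 months on study, then every 6 weeks thereafter". After treatment stops, Table 5.1-4 says "Both the Lung Cancer Symptom Scale and EQ-5D will be given in FU Visits 1 & 2", with "X01 = 35 days ± 7 days from last dose, X02 = 80 days ± 7 days from X01". Section 3.5 moves the first of these visits later in some cases, to a date "coinciding with the date of discontinuation (+/- 7 days) if the date of discontinuation is greater than 35 days after the last dose".

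**What happens in a hold.** Section 4.5.3.2 delays all blinded drugs for listed drug-related events and asks for re-evaluation weekly or more often. Section 4.5.3.3 says "Subjects may resume treatment with blinded study therapy when the drug-related AE(s) resolve to Grade" 1 or lower, or to baseline, with exceptions. The ordinary limit is 42 days from the last dose. Section 4.5.3.4 lets prolonged steroid tapers exceed it, with no stated maximum. That section also says "Tumor assessments for all subjects should continue as per protocol even if blinded study therapy dosing is delayed" and keeps safety and laboratory visits at least every 6 weeks. No sentence does the same for questionnaires.

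**What is analysed.** SAP 7.11.1: "Baseline and change from baseline of the average symptom burden index score at each assessment point will be summarized using descriptive statistics". It also gives TTSD hazard ratios, TTSD rates at Weeks 6, 12 and 24, and a completion rate whose denominator is subjects still on treatment or in follow-up.

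**The concern.** The questionnaires follow the dosing clock, and that clock stops when a toxicity is bad enough to delay treatment. Scheduled observation is therefore thinnest when a treatment-related burden is likely to be greatest. Protocol 5.7 collects these data to describe the effect of treatment from the subject's side and to feed cost-effectiveness models, so a gap of this kind bears on their purpose.

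The hold rules are the same in all blinded arms. A bias between arms therefore needs holds to be more frequent in one arm. That is a reasonable expectation for two active immunotherapies against saline or dextrose, though the documents do not quantify it. Missing data would then depend on both arm and symptoms.

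Two further mismatches follow. Doses are delayed and not skipped, so dosing visits drift from calendar time while TTSD rates are read at fixed weeks. And a subject on hold counts as expected in the completion rate although the schedule asks for no questionnaire.

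**Working it through.** The plan states no figure on this point, so there is none to reproduce. The check has three parts.

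**1. What continues during a hold**

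| Activity | Rule in a hold | Source |
|---|---|---|
| Tumor assessment | stays on schedule | Protocol 4.5.3.4 |
| Re-evaluation | weekly or more often | Protocol 4.5.3.2 |
| Safety and laboratory visits | at least every 6 weeks | Protocol 4.5.3.4 |
| Pregnancy test | at least every 4 weeks regardless of dosing | Tables 5.1-2, 5.1-3 |
| LCSS, EQ-5D | on treatment day, before the dose; nothing said about a hold | Tables 5.1-2, 5.1-3 |

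The protocol separates an assessment from dosing in several places, but not for the questionnaires.

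**2. Length of the gap**

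Planned questionnaire days are 1, 15, 22, 29, 43, 57, 64, 71, 85, then every 14 days to month 6, so planned intervals are 7 to 14 days. With last dose on day d and resumption at the ordinary limit, the gap runs from d to d + 42.

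| Last dose (day) | Resumes by (day) | Planned days inside the gap |
|---|---|---|
| 1 | 43 | 15, 22, 29 |
| 15 | 57 | 22, 29, 43 |
| 22 | 64 | 29, 43, 57 |
| 29 | 71 | 43, 57, 64 |
| 43 | 85 | 57, 64, 71 |
| 57 | 99 | 64, 71, 85 |
| 64 | 106 | 71, 85, 99 |
| 71 | 113 | 85, 99 |
| 85 | 127 | 99, 113 |

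A steroid taper can lengthen the gap. For a subject who discontinues, follow-up visit 1 falls 35 ± 7 = 28 to 42 days after the last dose (later if discontinuation is later). Follow-up visit 2 falls nominally on day 35 + 80 = 115, range 101 to 129. Neither depends on whether the toxicity has resolved.

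**3. Illustration of a possible effect on TTSD**

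All inputs except the sample size are assumptions:
- 277 subjects per arm (832 / 3);
- disease-driven TTSD exponential with median 4 months in both arms, which is 4 × 30.4375 / 7 = 17.4 weeks;
- holds in 30% of one active arm and 5% of placebo;
- a share q of holds brings symptom deterioration, uniform over weeks 2 to 12.

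At q = 0.5 this gives 277 × 0.30 × 0.5 = 41.6 hold-period deteriorations against 277 × 0.05 × 0.5 = 6.9.

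Share of the active arm's first deteriorations that fall in a hold:
- The chance that disease deterioration has not come first, averaged over weeks 2 to 12, is (17.39 / ln 2) × (2^(−2/17.39) − 2^(−12/17.39)) / 10 = 0.76.
- The numerator is 0.30 × q × 0.76, which is 0.114 at q = 0.5.
- Without censoring the denominator is 1, so the share is 11%.
- With censoring at 26 weeks, P(disease event by then) = 1 − 2^(−26/17.39) = 0.645. The denominator is 0.645 + 0.15 × 0.355 = 0.698, and 0.114 / 0.698 = 16%.
- At q = 0.2 with that censoring: 0.0457 / (0.645 + 0.06 × 0.355) = 7%.

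Cox hazard ratios from simulated trials under these inputs:

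| Setting | True HR, approx. | Seen if none captured |
|---|---|---|
| q = 0.5, censored at 26 weeks | 1.15 to 1.17 | about 1.0 |
| q = 0.5, no censoring | 1.10 to 1.11 | about 1.0 |
| q = 0.2, censored at 26 weeks | 1.06 | about 1.0 |
| q = 0.2, no censoring | 1.05 | about 1.0 |

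If half the hold-period deteriorations are captured about four weeks late, a true 1.17 is seen as about 1.07. The value of 1.0 in the last column is built in: the arms differ only by the hold-period events, and that column removes all of them.

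**The case against.** A reader might infer that quality of life is sampled only once toxicity has resolved, that deterioration in a hold is never observed, and that TTSD is biased by a known amount. The documents do not support any of these.

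- **Toxicity is sampled on dosing days.** Grade 2 fatigue does not trigger a hold, and fatigue is an LCSS item (Protocol 5.7). Dosing may resume at Grade 1, with Grade 2 fatigue, or with Grade 2 skin toxicity if there has been no Grade 3 skin event.
- **Much severe toxicity ends treatment.** Under Section 4.5.3.4 many Grade 3 and most Grade 4 drug-related events lead to discontinuation. Those subjects complete both instruments at follow-up visits 1 and 2. A deterioration that lasts to resumption is also recorded, only later.
- **Not scheduled is not the same as forbidden.** A site could give the questionnaire at a visit where the dose is then withheld.
- **Some holds are silent.** Several triggers are laboratory abnormalities, which need not move LCSS symptoms.
- **The TTSD definition is redacted.** If it required sustained worsening, a brief episode might not count.
- **The SAP does not define its assessment points as dosing-visit labels.** Mock-ups sit in a Data Presentation Plan that is not available here.
- **The analyses are descriptive or exploratory**, and outside the hierarchy in SAP 7.5.3.

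All of this stands, and it limits the claim. It does not remove the gap: a toxicity that triggers a hold and then settles has no scheduled questionnaire at its worst, although the subject is being seen.

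**Conclusion.** The concern holds in a limited form. The schedule gap is certain from the text; a bias between arms is possible but not shown. It needs holds to be more frequent on active treatment, some of them to bring symptoms that LCSS or EQ-5D would register, and those symptoms to fade before the next questionnaire. If so, the direction favours the more toxic arm.

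The illustration spans a true hazard ratio of 1.05 to 1.17 under assumed hold rates of 30% and 5%. It is no estimate for this trial. The gap matters most in early treatment, when planned questionnaires are 7 to 14 days apart. After month 6 they are 6 weeks apart, so an ordinary hold covers at most one. The OS and PFS analyses do not use these data. The point is worth correcting because the correction is cheap.

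**What to change.** **Protocol Tables 5.1-2 and 5.1-3.** Reword the questionnaire notes so that LCSS and EQ-5D are completed at the scheduled week from randomization whether or not a dose is given. During a hold, use the re-evaluation and safety visits already required. EQ-5D could be taken by telephone, as Table 5.1-4 already allows at survival visits. No dosing rule changes.

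**SAP 7.11.** Assign questionnaires to windows by week from randomization. Reconcile the completion-rate denominator with the questionnaires actually scheduled. Report questionnaire missingness during holds by arm.

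**Cost.** A few more questionnaires at existing contacts, plus table wording and SAP programming. With 832 subjects already accrued over 28 months at this amendment, the collection change helps only those still on treatment and does little for subjects past their early cycles. For them the windowing and the missingness report are what can still be done; neither needs new data.

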5.1.1 Retesting During Screening

Retesting of laboratory parameters and/or other assessments within the Screening period will be permitted (in addition to any parameters that require a confirmatory value).

Any new result will override the previous result (ie, the most current result prior to Randomization) and is the value by which study inclusion will be assessed, as it represents the subject's most current, clinical state.

Laboratory parameters and/or assessments that are included in [Table 5.1-1](#), Screening Procedural Outline may be repeated in an effort to find all possible well-qualified subjects. Consultation with the Medical Monitor may be needed to identify whether repeat testing of any particular parameter is clinically relevant.

5.2 Study Materials

The following materials will be provided to the site by BMS.

- NCI CTCAE version 4.0
- Nivolumab Investigator Brochure
- Ipilimumab Investigator Brochure
- Pharmacy Binder
- Laboratory manuals for collection and handling of blood (including biomarker and immunogenicity) and tissue specimens
- Site manual for operation of interactive voice response system, including enrollment worksheets
- Imaging Manual for image acquisition and submission to central vendor
- Manual for entry of local laboratory data
- Pregnancy Surveillance Forms
- Serious Adverse Events (or eSAE) case report forms
- Lung Cancer Symptom Score and EuroPRO Group's EQ-5D questionnaires

5.3 Safety Assessments

Safety assessments include AEs, physical examinations, vital signs, ECOG performance status, assessment of signs and symptoms, laboratory tests, pregnancy tests as outlined in [Section 5.1](#).

Some of the previously referred to assessments may not be captured as data in the eCRF. They are intended to be used as safety monitoring by the treating physician. Additional testing or assessments may be performed as clinically necessary or where required by institutional or local regulations.

5.3.1 Imaging Assessment for the Study

Any incidental findings of potential clinical relevance that are not directly associated with the objectives of the protocol should be evaluated and handled by the Study Investigator as per standard medical/clinical judgment.

5.4 Efficacy Assessments

Study evaluations will take place in accordance with the flow charts in [Section 5.1](#).

Contrast-enhanced computed tomography (CT) of the chest and CT or magnetic resonance imaging (MRI) of abdomen, and any other known or suspected sites of disease are the preferred methods of radiographic assessment of tumors. Repeat CT/MRI of pelvis is required for subjects with pelvic metastases at baseline, or if clinically indicated. Brain MRI scan is the preferred imaging method for evaluating CNS metastasis, and assessment is required at screening, however CT of the brain is acceptable if MRI is contraindicated. If a subject has a known allergy to contrast material, please use local prophylaxis standards to obtain the assessment with contrast if at all possible, or use the alternate modality. In cases where contrast is strictly contraindicated, a non-contrast scan will suffice.

All known or suspected sites of disease (including CNS) should be assessed at screening and at subsequent assessments using the same imaging method and technique. If more than one method is used at screening, then the most accurate method according to RECIST 1.1 should be used when recording data, and should again be used for all subsequent assessments.

Bone scan, PET scan, or ultrasound are not adequate for assessment of RECIST 1.1 response. In selected circumstances where such modalities are the sole modality used to assess certain non target organs, those non target organs may be evaluated less frequently. For example, bone scans may need to be repeated only when complete response is identified in target disease or when progression in bone is suspected.

Previously treated CNS metastases are not considered measurable lesions for purposes of RECIST 1.1 response. Subjects with a history of brain metastasis should have surveillance MRI/CT approximately every 6 weeks up to 36 weeks and then every 12 weeks, or sooner if clinically indicated.

Baseline assessments should be performed within 21 days of randomization.

Subjects will be evaluated for tumor response beginning 6 weeks from the date of randomization (± 5 days), then every 6 weeks (± 5 days) thereafter up to 36 weeks. Beyond Week 36, tumor assessments will be performed every 12 weeks (± 5 days), or more frequently as clinically indicated or per local Standard of Care, until disease progression (or until discontinuation of study drug in subjects receiving blinded study therapy beyond progression), lost to follow-up, withdrawal of study consent, or the study ends. See [Table 5.4-1](#) for a schedule of tumor assessments. Tumor assessments for all subjects should continue as per protocol even if dosing is delayed. Tumor measurements should be made by the same investigator or radiologist for each assessment whenever possible.

Tumor imaging assessments for ongoing study treatment decisions will be completed by the investigator using RECIST 1.1 criteria; see [Appendix 3](#).

Table 5.4-1: Schedule of CT/MRI Tumor Assessments

Time On Study	Assessment Frequency	Assessment Week (Day 1 of Week Shown)	Assessment Window
Baseline		Week 0	- 21 days
Between Week 6 and Week 36	Every 6 weeks	6, 12, 18, 24, 30, 36	± 5 days
Beyond Week 36	Every 12 weeks	48, 60, 72+	± 5 days

